Factors Affecting Mortality in Critical Patients Admitted to Intensive Care Unit Due to Coronavirus Disease 2019

NCT number: NCT04659876

Date: 11.09.2020

Study Design, Population, and Data

Critical patients hospitalized due to COVID-19 in ICU of the University of Health Sciences Turkey, Diyarbakır Gazi Yaşargil Training and Research of Hospital between March 22 and September 1, 2020, were included in this study. The study was approved by the Ethics Committee of University of Health Sciences Turkey, Diyarbakır Gazi Yaşargil Training and Research of Hospital (No: 550, 11.09.2020). The trial was registered with clinicaltrials.gov (NCT04659876). This retrospective cohort study was conducted in accordance with the 2008 Declaration of Helsinki criteria.

Critical patients diagnosed with COVID-19 on the dates specified, followed up in ICU, aged >18 years, in serious need of oxygen support according to WHO and the temporary guidelines of T.C. Science Board of the Ministry of Health [presence of fever, muscle/joint pain, cough, and sore throat; tachypnea (30 breaths/min) or dyspnea; use of extra respiratory muscles; SpO₂ level below of ≤90% in room air; bilateral diffuse pneumonia symptom detected on chest radiography or computerized tomography (CT); and PaO₂/ FiO₂ ratio of <300], and developed or had complications including severe pneumonia, ARDS, sepsis/septic shock, and acute renal failure were included in the study. Patients with COVID-19 aged <18 years with mild-to-moderate symptoms, no respiratory distress, and no signs of diffuse pneumonia on chest X-ray or CT as well as ICU patients excepted from COVID-19 diagnosis were excluded from the study. In addition, patients whose complete data could not be accessed from the hospital system or the patient file records were excluded. When the patients were admitted to ICU for the first time, their clinical conditions were evaluated with APACHE II and SOFA scores, and the degree of renal failure was evaluated using the Kidney Disease: Improving Global Outcomes (KDIGO) classification. Age; sex; comorbidity; ABO and Rh blood groups; APACHE II and SOFA scores and KDIGO stage during admission to ICU; hemogram parameters [white blood cell (WBC), neutrophil, lymphocyte, neutrophil/lymphocyte (N/L) ratio, hemoglobin, hematocrit, and platelet count]; blood gas values [pH, partial oxygen pressure (PO₂), partial carbon dioxide pressure (PCO₂), bicarbonate (HCO₃), and lactate]; coagulation parameters [prothrombin time (PTZ) and D-dimer]; blood biochemistry results [creatinine kinase (CK), lactate dehydrogenase (LDH), C-

reactive protein (CRP), urea, creatinine, alanine aminotransferase (ALT), aspartate aminotransferase (AST), total bilirubin, direct bilirubin, and indirect bilirubin]; and procalcitonin (PCT) and ferritin levels of the patients were recorded. Moreover, the length of stay in ICU and whether the patient died or survived were recorded. Patient data were rechecked for erroneous information before the last data entry and entered into a computerized database.

Patients were divided into two groups—those who survived (Survivors) and those who died (Non-survivors) during ICU follow-up. Both groups were compared in terms of clinical characteristics; APACHE II and SOFA scores and KDIGO stage; and laboratory values at the first admission to ICU. We attempted to determine the factors that affect mortality in critically ill patients hospitalized in ICU with COVID-19 diagnosis.

Statistical Analysis

SPSS 16.0 software for Windows (SPSS Inc., Chicago, IL, USA) was used for statistical analysis. Continuous data were expressed as means (SD or minimum–maximum), and categorical data were expressed as frequencies with percentages. Comparison of categorical data in the groups was performed using chi-square and Fisher's exact test, and the results were presented as n%. Kolmogorov–Smirnov test was used to determine whether the numerical data fit the normality distribution. Data conforming to the normality distribution were evaluated using Student t-test, and Mann–Whitney U and Kruskal–Wallis tests were employed to compare data that did not fit the normality distribution. Binary logistic regression was performed for the risk factors that were found to be significant in the univariate analysis. Odds ratio (OR) with 95% confidence interval (CI) was used to report the association between mortality and exposure to the risk factors. In all comparisons, P value of <0.05 was considered significant.

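### ICU admission date is not a candidate covariate over a 5.4-month accrual window, so a marker that also drifted could pick up a change in mortality not captured by measured severity

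*Combined protocol and SAP*

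**What the plan says.** Study Design, Population, and Data describes a single-centre, non-randomised design ("This retrospective cohort study was conducted in accordance with the 2008 Declaration of Helsinki criteria") covering ICU patients "between March 22 and September 1, 2020, were included in this study". The severity criteria are referred to WHO and to the "temporary guidelines of T.C. Science Board of the Ministry of Health".

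The list of recorded variables begins "Age; sex; comorbidity; ABO and Rh blood groups; APACHE II and SOFA scores and KDIGO stage during admission to ICU" and goes on through haematology, blood gases, coagulation, biochemistry, procalcitonin and ferritin. It closes with "Moreover, the length of stay in ICU and whether the patient died or survived were recorded". Neither admission date nor any treatment is listed.

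The last paragraph before Statistical Analysis sets out the comparison of survivors with non-survivors at entry to the ICU: "Both groups were compared in terms of clinical characteristics; APACHE II and SOFA scores and KDIGO stage; and laboratory values at the first admission to" (that unit). Its stated aim is to identify what affects mortality.

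Statistical Analysis then says: "Binary logistic regression was performed for the risk factors that were found to be significant in the univariate analysis". The effect measure follows: "Odds ratio (OR) with 95% confidence interval (CI) was used to report the association between mortality and exposure to the risk factors". No covariate is forced into the model, and no stratified or sensitivity analysis by calendar time is described.

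**The concern.** In a non-randomised cohort whose only aim is to find factors that affect mortality, control of confounding is the central question of validity. Calendar time can confound the result if two things happen together: the risk of death changes over the window, and the admission level of a marker changes too. Pooling then produces an association between marker and death even if there is none at any given time. Drift in the opposite direction can hide a real association.

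A variable that is never offered to the univariate screen cannot enter the model, so the plan has no direct way to detect or remove this. Because no treatment variable is recorded, nothing else in the model represents changes in care directly. The screen is also wide. Counting comorbidity as one item, the recorded admission variables number 8 (demographics, blood groups, scores, KDIGO stage) + 7 (haemogram) + 5 (blood gases) + 2 (coagulation) + 10 (biochemistry) + 2 (procalcitonin, ferritin) = 34. A drifting marker therefore has many chances to be selected at P<0.05.

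**Working it through.** **No figure to reproduce.** The documents give no sample size, number of deaths, mortality or power. Only the window can be computed from them. Everything else below is an assumption, shown over a range.

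**Window.** 22 March to 1 September 2020 is 163 days; 163 / 30.44 = 5.4 months.

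**Check 1: is a change in mortality enough by itself?** Take two equal calendar halves with mortality m1, m2 and a binary marker of prevalence q1, q2 that has no effect on death within either half. The pooled cell proportions are:

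- marker present, died: a = ½(q1·m1 + q2·m2)
- marker present, survived: b = ½[q1(1−m1) + q2(1−m2)]
- marker absent, died: c = ½[(1−q1)m1 + (1−q2)m2]
- marker absent, survived: d = ½[(1−q1)(1−m1) + (1−q2)(1−m2)]

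The crude OR is ad/(bc). With mortality 70% then 40% and prevalence 50% in both halves, a = c = 0.275 and b = d = 0.225, so OR = 1.00. A fall of 30 percentage points in mortality does no harm if the marker is stable.

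When both shift:

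| Mortality | Marker prevalence | Calculation | Crude OR | Approx. chance of P<0.05 at N=100 / 200 / 400 |
|---|---|---|---|---|
| 60% → 40% | 60% → 40% | 0.26×0.26 / (0.24×0.24) | 1.17 | 6% / 8% / 12% |
| 60% → 40% | 70% → 30% | 0.27×0.27 / (0.23×0.23) | 1.38 | 12% / 20% / 36% |
| 70% → 40% | 70% → 30% | 0.305×0.255 / (0.195×0.245) | 1.63 | 22% / 40% / 68% |
| 70% → 40% | 80% → 20% | 0.32×0.27 / (0.18×0.23) | 2.09 | 44% / 73% / 95% |

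**Check 2: a continuous marker, alone in the logistic model.** Simulation with 2000 replicates per cell, two equal periods and a marker with no effect within a period; OR per SD. Where a range is given, repeat runs differed slightly.

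| Mortality | Marker shift | OR | False positives, n=150 | False positives, n=250 |
|---|---|---|---|---|
| 55% / 45% | 0.3 SD | 0.97 | 5% | 5% |
| 60% / 40% | 0.5 SD | 0.91 | 8–9% | 12% |
| 65% / 35% | 0.8 SD | 0.79–0.80 | 27% | 40–43% |

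With a period term added, the OR is 1.00 and the rejection rate 4–6% in every cell. This follows from the set-up, because the marker was given no effect within a period. It shows what the term does and is not evidence about this cohort.

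**Check 3: drift carried entirely by a measured severity score.** Here n=150, with 2000 replicates and no period term. With mortality about 60%/40% and a 0.5 SD shift, the crude OR is 0.91 with 9–10% rejection; once the score is in the model, 1.00 and 5%. With about 65%/35% and 0.8 SD, the crude OR is 0.79 with 28%; with the score, 1.00 and 5%.

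**Cost of an unneeded term.** With no drift and n=150, adding period raised the marker's standard error by about 0.7%.

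**The case against.** The strongest case against is that this is a generic omission, found in many cohorts accrued over months, with no sign in the documents that it did harm. Four points deserve weight.

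- **Any change in mortality might be read as enough to create a false marker effect.** It is not. Check 1 shows that the marker must drift as well.
- **A reader might infer that criteria or care did change**, from the word for temporary in the guideline reference or from outside knowledge of the pandemic. The documents do not support this. The word describes the guideline's status, and the protocol lists one set of entry criteria with no versions or dates. Nothing is said about mortality, care or marker levels over time.
- **A reader might infer that the planned model has no protection at all.** Age, comorbidity, APACHE II, SOFA, KDIGO stage, blood gases and lactate are all candidates. If they pass the screen, drift that acts through measured case mix is largely removed (Check 3).
- **The false-positive rates of 27% to 43% might be taken as those of the final regression.** They describe a model with the marker alone, and need a swing of 30 percentage points in mortality together with a 0.8 SD shift in the marker. Neither is anchored in the documents.

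All four limit the size and certainty of the point. They do not remove it. Drift due to changing care would not be captured by admission severity, and no recorded variable represents it. Whether APACHE II, SOFA or age enters the model is itself left to the screen. The further objection that model degrees of freedom may be scarce is fair, because the number of deaths is unknown. It bears on the form of the remedy.

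**Conclusion.** The point holds in a limited form. Over a 163-day window, admission date or period can never enter the model as planned, so confounding by calendar time that is not carried by measured severity is neither adjusted for nor visible to a reader. Under the assumed shifts, the consequence for a marker with no effect ranges from nothing of note (OR 0.97, 5% rejection) to a material distortion (OR about 0.79 with 27% rejection at n=150; 40–43% at n=250). It is smaller where the severity scores or age carry the drift. Where this study falls in that range cannot be determined from the documents, which neither show nor exclude drift. The case for acting rests on the low cost of the remedy rather than on evidence of bias: it is a worthwhile improvement, and does not show that the planned odds ratios are wrong.

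**What to change.** 1. Add ICU admission date to the recorded variables. It must be obtainable for every patient, because inclusion is defined by date and ICU length of stay cannot be derived without it.
2. Report admissions and ICU mortality by calendar period, so that readers can see whether mortality moved.
3. Include one prespecified calendar term, either linear date or early/late, in the logistic regression whatever its univariate P value. If there are too few deaths to afford it, present the model with that term as a sensitivity analysis.

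The cost is one sentence in Statistical Analysis, one small table, one model degree of freedom and slightly wider confidence intervals if period proves irrelevant. A single term has limits: an early/late split leaves drift within each half uncorrected, and a linear term captures only a steady trend.

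### Does the undated complication clause in the inclusion criteria let events after ICU admission decide who is in the cohort?

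*Combined protocol and SAP*

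**What the plan says.** All the relevant text is in the combined protocol and SAP, under Study Design, Population, and Data and in the group-comparison paragraph just before Statistical Analysis.

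- **Cohort.** Critical COVID-19 patients in the ICU of one hospital "between March 22 and September 1, 2020, were included in this study". The design is retrospective, and ethics approval is dated 11.09.2020, after the window closed.
- **Inclusion.** Adults followed up in ICU in serious need of oxygen. A bracketed list includes SpO₂ of 90% or less in room air, PaO₂/FiO₂ below 300 and "bilateral diffuse pneumonia symptom detected on chest radiography or computerized tomography (CT"). Joined to this by *and* is the clause at issue: patients who "developed or had complications including severe pneumonia, ARDS, sepsis/septic shock, and acute renal failure were included in the study".
- **Exclusion.** Age under 18 with milder disease and no respiratory distress or diffuse pneumonia; no COVID-19 diagnosis; incomplete records. Absence of a complication is not listed.
- **Predictors.** "When the patients were admitted to ICU for the first time, their clinical conditions were evaluated with APACHE II and SOFA scores". KDIGO stage is taken at the same point. The group comparison uses "laboratory values at the first admission to ICU".
- **Outcome.** Two groups: "those who survived (Survivors) and those who died (Non-survivors) during ICU follow-up".
- **Aim.** To "determine the factors that affect mortality in critically ill patients hospitalized in ICU with COVID-19 diagnosis".

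**The concern.** The plan ties the scores, KDIGO stage and laboratory values to first ICU admission but attaches no date to the complication clause. *Developed*, beside *had*, in patients followed up in ICU, can cover onset during the stay. The whole ICU course was on file when patients were selected, so a later complication could have counted towards entry.

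That would be selection on an event after baseline. Later sepsis or renal failure depends on admission severity and is related to death. Admitting patients because of it, while leaving out comparable patients who stayed free of it, can distort the odds ratios for severity and laboratory markers (usually towards 1) and raise the cohort's mortality. The argument does not extend to age, sex or blood group.

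The missing one-or-all rule adds to this. If all four complications were required, acute renal failure would be an entry condition while KDIGO stage is also a compared predictor.

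**Working it through.** The documents give no sample size, event count or complication rate, so there is no figure of the plan's to reproduce. The check has two parts.

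**1. Reading the text**

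- The complications follow the word *including*, which introduces examples in an open list. All members of an open list cannot be required, so the natural reading is any complication of this kind.
- The same sentence already asks for serious oxygen need, SpO₂ of 90% or less, PaO₂/FiO₂ below 300 and bilateral diffuse pneumonia. In substance these lie close to two of the listed complications, severe pneumonia and ARDS. A patient who meets them at admission has, in nearly every case, met the clause too.
- Lack of a complication is not an exclusion, the opening paragraph and the aim describe critical COVID-19 patients in ICU generally, and later complications are not among the recorded variables. None of this suggests a filter applied to the later course.

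**2. How large could the bias be?**

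All inputs here are assumptions: a binary admission predictor with prevalence 50% and true OR 2.00; mortality 40% without the predictor; a later complication in 80% of those who die and 20% of survivors. Mortality with the predictor follows from odds (0.4/0.6) × 2 = 1.333, that is 57.1%, so overall mortality is (40% + 57.1%)/2 = 48.6%.

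Let a_x be the share already qualifying at admission (x = 1 with the predictor, 0 without) and l_d the probability of a later complication (d = 1 died, 0 survived). Then:

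- probability of inclusion: s_xd = a_x + (1 − a_x) × l_d
- observed OR = true OR × (s_11 × s_00)/(s_10 × s_01)

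For a_0 = 95%, a_1 = 98%:

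- s_11 = 0.98 + 0.02 × 0.8 = 0.996; s_10 = 0.98 + 0.02 × 0.2 = 0.984
- s_01 = 0.95 + 0.05 × 0.8 = 0.990; s_00 = 0.95 + 0.05 × 0.2 = 0.960
- factor = (0.996 × 0.960)/(0.984 × 0.990) = 0.982; observed OR = 1.96
- share included = 0.5 × (0.4 × 0.990 + 0.6 × 0.960) + 0.5 × (0.571 × 0.996 + 0.429 × 0.984) = 98.1%, so 1.9% are left out

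For a_0 = 40%, a_1 = 70%: factor = (0.94 × 0.52)/(0.76 × 0.88) = 0.731; observed OR = 1.46.

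| Qualify at admission (without / with predictor) | Observed OR | Cohort entering only through a later event | Eligible patients left out | Cohort mortality (all eligible 48.6%) |
|---|---|---|---|---|
| 98% / 99% | 1.99 | 0.7% | 0.8% | 48.8% |
| 95% / 98% | 1.96 | 1.7% | 1.9% | 49.2% |
| 80% / 90% | 1.86 | 7.7% | 7.9% | 51.2% |
| 40% / 70% | 1.46 | 28% | 24% | 58.2% |
| 20% / 50% | 1.29 | 47% | 34% | 64.2% |

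If later complications are unrelated to death (20% or 50% in both outcome groups), the OR stays at 2.00.

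A simulation with a continuous marker gives the same picture. There the OR per SD in all eligible patients was 1.69 to 1.79, with 50% mortality. With 90% qualifying at admission, the entered cohort had an OR of 1.63 to 1.79 and mortality of 51% to 52%. With 30% qualifying, the OR was 1.39 to 1.78 and mortality 58% to 65%. The direction is not uniform: in one setting the OR rose from 1.70 to 1.78.

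A bound that needs no model: if a share e of eligible patients is left out, mortality is overstated by at most e times the mortality of those included. At an assumed included mortality of 60%, that is 0.02 × 60 = 1.2 points for e = 2% and 0.05 × 60 = 3 points for e = 5%.

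**The case for a change.** The strongest reply is that the reading is inferred, not written. The bracketed oxygenation and imaging criteria carry no date either, so it is not proved that patients met them at admission. A patient who meets every bracketed criterion but has no complication fails inclusion, yet matches no exclusion. If all four complications were required, later sepsis or renal failure could decide entry for many patients, and one sentence would then span anything from no effect to a substantial one.

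What stands is the textual gap. Nothing in the documents dates the criteria, and the gap covers the bracketed list as well as the complication clause.

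The rest carries less weight. The all-four reading sits badly with an open list, and the KDIGO overlap depends on it entirely. The rows with large bias leave out about a quarter to a third of otherwise eligible ICU patients, which is hard to reconcile with a cohort this hypoxaemic and with exclusions that never mention lack of a complication. Overstated mortality also matters less here, because the stated aim is factors affecting mortality and no mortality rate is named as an objective.

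**Conclusion.** This is missing detail that an analyst fills sensibly: judge eligibility at first ICU admission, where the plan already anchors its scores and laboratory values, and accept any one complication. Read that way, the plan gives essentially the same cohort and odds ratios as a version with the time point written in. With 95% or more qualifying at admission, the illustrative OR moves from 2.00 to no lower than 1.96 and mortality by 49.2 − 48.6 = 0.6 points at most.

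Dropping the criterion and re-screening the ICU admissions of the window would cost chart review, and would leave the patient set unchanged if the clause never bound. A cohort restricted to complicated disease, judged at admission, is also a legitimate choice.

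The conclusion rests on the any-one reading and on most patients meeting the bracketed criteria on arrival. The documents support the first by their wording and make the second likely, but do not prove either. They give no share qualifying at admission, so the figures above show scale only. A sentence in the study report on when eligibility was judged would be good practice; the plan need not change for it.

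### KDIGO stage is analysed as a mortality factor with the staging system and reference creatinine unstated, and chronic kidney disease would be adjusted for only if it passes a univariate screen

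*Combined protocol and SAP*

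**What the plan says.** All references are to the combined protocol and SAP.

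Under Study Design, Population, and Data, renal status is graded at first ICU admission: "the degree of renal failure was evaluated using the Kidney Disease: Improving Global Outcomes (KDIGO) classification". The recorded items include "Age; sex; comorbidity; ABO and Rh blood groups; APACHE II and SOFA scores and KDIGO stage during admission to ICU". Among the biochemistry results they also include "urea, creatinine, alanine aminotransferase (ALT), aspartate aminotransferase (AST". Chronic disease appears only as the single word comorbidity. No pre-illness creatinine, urine output, chronic kidney disease or dialysis item is listed.

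Acute renal failure is an eligibility complication, without a definition: patients who "developed or had complications including severe pneumonia, ARDS, sepsis/septic shock, and acute renal failure were included in the study". The exclusions cover age with mild disease, patients without a COVID-19 diagnosis, and incomplete records ("patients whose complete data could not be accessed from the hospital system or the patient file records were excluded"). None concerns chronic kidney disease or dialysis.

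The same section then sets out the survivor comparison, on values at ICU entry: "Both groups were compared in terms of clinical characteristics; APACHE II and SOFA scores and KDIGO stage; and laboratory values at the first admission to". Under Statistical Analysis, factors significant at P <0.05 in the univariate analysis go into a binary logistic regression, reported as odds ratios with 95% confidence intervals. No covariate is forced in, and no renal sensitivity analysis is planned.

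**The concern.** KDIGO stage is one of three severity measures named for the comparison of survivors and non-survivors. Its meaning depends on two things the plan leaves out: which KDIGO staging was used (acute or chronic), and what each patient's creatinine was compared with.

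A patient with stable advanced kidney disease, or on maintenance dialysis, who is admitted for COVID-19 pneumonia could be recorded at a high stage without any new renal injury. Such patients would then sit in the same stages as patients with new organ failure. Admission creatinine and urea would be raised in both groups, so they cannot separate them.

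The plan's only route to separating them is the comorbidity item, and that item enters the model only if it is significant on its own. At stake is whether an odds ratio for KDIGO stage can be read as the effect of acute renal failure, of pre-existing kidney disease, or of a mixture.

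**Working it through.** The plan states no sample size, event count, renal event rate or chronic-kidney prevalence, so there is no figure of its own to reproduce. Every input below is assumed and serves only to show direction and plausible size.

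**Step 1: a two-by-two that can be checked by hand.** Assume acute injury in 30% of patients with 70% mortality, stable chronic disease without acute injury in 10%, and neither in 60% with 40% mortality. All chronic patients are scored as acute.

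- *Chronic mortality 40%.* Correct odds ratio: (0.70/0.30)/(0.40/0.60) = 3.50. Mortality in those scored acute: (0.30×0.70 + 0.10×0.40)/0.40 = 0.625. Observed odds ratio: (0.625/0.375)/(0.40/0.60) = 2.50.
- *Chronic mortality 80%.* Mortality without acute injury: (0.60×0.40 + 0.10×0.80)/0.70 = 0.457. Correct odds ratio: (0.70/0.30)/(0.457/0.543) = 2.77. Mortality in those scored acute: (0.30×0.70 + 0.10×0.80)/0.40 = 0.725. Observed odds ratio: (0.725/0.275)/(0.40/0.60) = 3.95.

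The same scoring error lowers the odds ratio in the first case and raises it in the second.

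**Step 2: per-stage model.** Assume log-odds of death = −0.4 + ln(1.8) × true acute stage + ln(ORc) × chronic. Acute stages 0/1/2/3 occur in 60/20/10/10% of patients, and chronic disease in 10%, independently. A chronic patient is recorded at the higher of the true acute stage and a value of 2 or 3 (equal chance). Logistic models were fitted to the expected cell frequencies, so there is no sampling error.

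| ORc (chronic disease) | Stage OR, no flag | Stage OR, flag in model | Univariate OR for chronic disease |
|---|---|---|---|
| 1 | 1.52 | 1.78 | 1.00 |
| 1.5 | 1.61 | 1.78 | 1.46 |
| 3 | 1.77 | 1.78 | 2.81 |
| 4 | 1.84 | 1.78 | 3.71 |
| 6 | 1.93 | 1.79 | 5.49 |

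The true value is 1.80. Excluding chronic patients returns it by construction, because everyone left is correctly staged. With ORc = 1, the no-flag value runs from about 1.6 at 5% prevalence to about 1.4 at 20%. Changing the intercept to −1.0 or 0.0 moves the no-flag column by no more than about 0.04.

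**Step 3: the screen.** In the first row attenuation is greatest (1.80 to 1.52) and the univariate odds ratio for chronic disease is 1.00, so the term passes P <0.05 only by chance. In the third row the univariate odds ratio is 2.81, so the term is far more likely to pass, yet including it changes the stage odds ratio only from 1.77 to 1.78. The screen works against the adjustment where it is most needed.

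**Step 4: share of the high stages affected.** Patients recorded at stage 2–3: 0.90×0.20 + 0.10 = 0.28. Chronic patients among them without stage 2–3 acute injury: 0.10×0.80 = 0.08, and 0.08/0.28 = 29%. If no chronic patient has any acute injury, the share is 0.10/0.28 = 36%. On that variant the no-flag stage odds ratios are 1.43, 1.69 and 1.86 for ORc of 1, 3 and 6. The univariate chronic odds ratio is then 0.68 at ORc = 1 and 1.01 at ORc = 1.5, where the stage odds ratio is 1.52. The pattern is similar, but the blind spot of the screen shifts to a slightly higher ORc.

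**The case against.** The strongest reply is that silence is not absence. The variable list shows what entered the database, not every input used in scoring. The plan says that "When the patients were admitted to ICU for the first time, their clinical conditions were evaluated with APACHE II and SOFA scores", yet it does not list inputs to those scores such as the Glasgow Coma Scale or mean arterial pressure, and nobody infers that they were ignored. Earlier creatinine values and urine output may have been available in the hospital system and used. This stands. A reader might infer that staging rested on a single admission creatinine; the documents do not say so. They show only that the rule is unstated.

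Second, degree of renal failure is not labelled acute. If overall renal dysfunction was meant, a chronic patient at a high stage is not misclassified. That also stands, but the variable then does not measure the acute failure named in the eligibility criteria, so the meaning still has to be stated.

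Third, a chronic-kidney comorbidity could enter the model beside KDIGO stage. It could, so the stronger inference that the study is unable to tell acute from pre-existing disease goes too far. But entry depends on the screen, and Step 3 shows why that is a weak safeguard.

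Fourth, the study is exploratory, with many candidate factors and no primary renal hypothesis, and every numerical input here is assumed. Both points are accepted. They limit the weight of the finding, but they do not answer it when the remedy is this cheap.

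**Conclusion.** The point holds as a worthwhile, inexpensive improvement. The staging system and reference creatinine are unstated, chronic kidney disease and dialysis are not separately identified, and adjustment for them is left to a univariate P value. If stable chronic disease was scored at high stages, the KDIGO odds ratio may be biased. On the Step 2 assumptions, a true 1.8 per stage would be estimated at between about 1.5 and 1.9, according to the risk that chronic disease itself carries, with almost no bias when its odds ratio is near 3.

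A reader might infer that the odds ratio must be attenuated; that follows only if chronic disease carries little mortality risk of its own. Neither the direction nor the size in this cohort can be derived from the documents, and whether any such mis-scoring occurred is unknown.

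**What to change.** 1. State which KDIGO staging was used, the source of the reference creatinine, and whether urine output contributed.
2. Stage acute injury against the most recent pre-illness creatinine where one exists. Where none exists, apply a stated fallback and flag those patients. A missing earlier value should not trigger the exclusion for incomplete records.
3. Derive a chronic kidney disease/maintenance dialysis flag from the comorbidity data and the records already abstracted.
4. Keep that flag in the logistic model whenever KDIGO stage, creatinine or urea is entered, whatever its univariate P value.
5. Repeat the renal analyses without flagged patients as a sensitivity analysis.

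The cost is one extra covariate and a look-up in records already in use. The drawback is that some patients will have no earlier creatinine and will depend on the fallback. If chronic kidney disease is already coded under comorbidity and a reference rule was applied, items 1 to 3 largely reduce to stating what was done.

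### PO2 is the only individual oxygenation variable recorded, without FiO2 or PaO2/FiO2, so its comparison by survival is hard to interpret if inspired oxygen differed between patients

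*Combined protocol and SAP*

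**What the plan says.** The Study Design, Population, and Data section describes existing-record research: "This retrospective cohort study was conducted". Its eligibility paragraph selects patients "in serious need of oxygen support" and names a PaO2/FiO2 ratio below 300 among the features. A room-air condition is attached only to the SpO2 criterion.

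The list of recorded variables in the same section contains "blood gas values [pH, partial oxygen pressure", followed by PCO2, bicarbonate and lactate. FiO2, PaO2/FiO2, SpO2, mode of oxygen delivery and sample type are not in that list. Severity at admission is recorded separately: "their clinical conditions were evaluated with APACHE II and SOFA scores". No component scores are listed. Incomplete records are dropped: "patients whose complete data could not be accessed from the hospital system or the patient file records were excluded".

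Survivors and non-survivors are compared on, among other things, "laboratory values at the first admission to ICU". The aim reads: "We attempted to determine the factors that affect mortality in critically ill patients hospitalized in ICU with COVID-19 diagnosis". The Statistical Analysis section sets significance at P<0.05 and builds the model by screening: "Binary logistic regression was performed for the risk factors that were found to be significant in the univariate analysis".

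**The concern.** The plan relates oxygenation to inspired oxygen when it describes who is eligible, but records only the unindexed PO2 for analysis. PO2 depends both on the lungs and on how much oxygen the patient was breathing. If clinicians gave more oxygen to patients with worse lungs, PO2 values in survivors and non-survivors are drawn together.

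Two things are then at stake. First, an odds ratio for PO2 would not describe lung function, and a larger sample does not cure that. Second, an attenuated PO2 may not reach P<0.05 in the univariate comparison and so never enter the regression. The SOFA total carries oxygenation only inside a sum, so it gives no separate odds ratio. The harm is confined to what the study can say about admission oxygenation, one of many exploratory factors.

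**Working it through.** **What the documents supply.** They give the recorded list, the screening rule and the 0.05 level (two-sided is assumed, as sidedness is not stated). They give no sample size, death rate, effect size, FiO2 distribution or sampling conditions. There is no stated figure to reproduce, and everything numerical below rests on assumptions.

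**Step 1: closed form.** On the log scale, log PO2 = log ratio + log FiO2. Suppose FiO2 offsets a fraction c of the differences in the ratio, with unrelated scatter of SD τ, and let σ be the SD of the log ratio. The correlation of log PO2 with the log ratio is then

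r = (1−c)σ / √[(1−c)²σ² + τ²],

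and the standardised survivor/non-survivor difference in PO2 is about r times that of the ratio. Take σ = 0.4 and a standardised difference of 0.63 for the ratio (from simulation: median ratio 140, values capped below 300, 50% deaths, OR 2 per SD lower ratio, FiO2 centred at 0.6 and limited to 0.21–1.0).

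- One FiO2 (c=0, τ=0): r = 1, difference 0.63. Simulated: 0.63.
- FiO2 unrelated to the lungs (c=0, τ=0.3): r = 0.4/√(0.16+0.09) = 0.80, difference 0.63×0.80 = 0.50. Simulated: 0.50.
- Half offset (c=0.5, τ=0.2): r = 0.2/√(0.04+0.04) = 0.71, difference 0.45. Simulated: 0.45.
- 80% offset (c=0.8, τ=0.2): r = 0.08/√(0.0064+0.04) = 0.37, difference 0.23. Simulated: 0.30.
- Full offset (c=1, τ=0.2): r = 0, difference 0. Simulated: 0.15.

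The last two simulated values are higher because FiO2 cannot leave 0.21–1.0, which limits how far it can offset. The formula also shows that partial titration without scatter (τ=0, c<1) costs little, since PO2 then still ranks patients as the ratio does. Simulation agrees: the PO2 odds ratio is 1.89–1.99 against a true 2.

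**Step 2: chance of passing the screen, with realistic FiO2.** An error-free ratio is too generous a comparator. The ratio here is PO2 divided by charted FiO2 with lognormal error (log-SD 0.25). Other assumptions: lognormal ratio, median 140, log-SD 0.4, truncated to 40–300; 45% deaths; OR 2 per SD; N=100; Mann–Whitney at 0.05. Titration is on the log scale towards a PO2 of about 75 mmHg.

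| FiO2 pattern | PO2 | Charted ratio | Charted ratio, 20% of FiO2 missing | Ratio minus PO2, points (complete; 20% missing) |
|---|---|---|---|---|
| One FiO2 | 88% | 75% | 64% | −13; −24 |
| Unrelated to lungs | 75% | 81% | 71% | +6; −4 |
| Half titration | 71% | 77% | 68% | +6; −3 |
| Three-quarters titration | 46% | 77% | 68% | +31; +22 |
| Full titration | 8% | 74% | 63% | +66; +55 |

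**Step 3: sensitivity.** The settings were varied over log-SD 0.35–0.45, deaths 35–50%, and different scatter designs. PO2 passes as follows (N=100 / N=200):

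- One FiO2: 82–90% / 99–100%.
- Unrelated: 58–75% / 87–97%.
- Half titration: 45–79% / 73–98%.
- Three-quarters: 20–58% / 33–90%.
- Full: 5–9% / 6–13%.

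The charted ratio passes 60–79% / 88–98% throughout. If a latent severity rather than the ratio itself drives death (N=200), PO2 against charted ratio is 61–88% against 66–90% (unrelated), 22–66% against 61–90% (three-quarters) and 5–13% against 61–90% (full). At OR 1.5 even an error-free ratio passes only 39–49% / 68–81%, so at that effect size many misses come from the screen itself.

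**The case against.** The strongest reply is that nothing in the documents shows the harmful case applies. Needing oxygen support makes differing FiO2 plausible, but says nothing about how tightly oxygen was titrated, and the benefit of the ratio depends on that. With weak titration, charting error and missing FiO2 cancel the gain. At one FiO2, the charted ratio does worse than PO2. This stands. A reader might infer that PO2 should be replaced by the ratio, or reduced to description if FiO2 is lost. The figures do not support that: with FiO2 unrelated to the lungs or half titrated, PO2 still passes 73–98% of the time at N=200.

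It can also be said that missing a factor at P<0.05 is partly a fault of univariate screening, that the severity scores already carry oxygenation, and that the plan states no oxygenation hypothesis. Each is true, and each limits the harm. None removes the problem of interpretation: a total score gives no separate odds ratio, and the reader cannot tell what a PO2 result means without the oxygen status.

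Finally, FiO2 may not be recoverable. The ratio threshold appears in a list of eligibility features, which suggests FiO2 was known for some patients but does not show that it was charted with every admission gas. The fix therefore needs a fallback.

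**Conclusion.** The concern holds in conditional form. PO2 is recorded as the only individual oxygenation variable, without the information needed to interpret it, in patients selected for needing oxygen. If FiO2 was raised in sicker patients, the PO2 comparison mixes lung function with oxygen given and may be missed at the screen. The loss is nil at one FiO2, modest when FiO2 was unrelated or half titrated, and large only under strong titration. Under the assumed inputs (N=100, OR 2), the shortfall of PO2 against a charted ratio runs from none to about 66 percentage points. That spread shows sensitivity to assumptions and is not an estimate for this study.

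A reader might also infer that the study will miss oxygenation as a risk factor, or that the plan concludes that oxygenation is unrelated to death. The documents support neither: they give no titration pattern or sample size, and draw no such conclusion. This is a cheap, worthwhile improvement and does not invalidate the analysis.

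**What to change.** - Extract FiO2 at the admission blood gas from the existing records, and state the sample type and the oxygen status at sampling. If all gases were on room air or at one FiO2, say so; PO2 then serves.
- Report PaO2/FiO2 alongside PO2, not in its place, in the survivor/non-survivor comparison.
- Report an odds ratio for the ratio in one prespecified supplementary model without SOFA, because the two overlap.
- Do not exclude patients for missing FiO2 alone. The existing rule on incomplete data would otherwise shrink the cohort. Report how many lack FiO2.
- If FiO2 cannot be recovered, keep the PO2 analysis, state the limitation, and do not take a non-significant PO2 as evidence that admission oxygenation is unrelated to mortality.

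The cost is limited chart extraction and one extra model, with no new patient procedure. The downside is that missing or imprecise FiO2 can cancel the gain if titration was weak, which is why both measures should be shown.
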